7.2.5 Adverse Event Action Taken

The investigator/designee will assess the action taken by the subject or the study staff in relation to the AE using the following classifications:

Action

1 = None

2 = Remedial therapy (more than 1 dose of medication required)

3 = Discontinued study

4 = Hospitalization
5 = Other

7.2.6 Adverse Event Outcome

The investigator/designee will assess the outcome of the AE, either at resolution or at the end of the study period, using the following classifications:

Outcome
1 = Resolved
2 = Continuing
3 = Continuing Chronic Condition
4 = Unknown, Off-Study before could confirm resolution of AE
5 = Death
6 = Unknown

7.2.7 Adverse Event Seriousness

The investigator/designee will categorize all AEs either as serious or non-serious, using the criteria defined in Section 7.1.6 of this protocol.

Any events defined as serious will also be reported following SAE reporting guidelines outlined in Section 7.3 of this protocol.

7.3 Adverse Event Reporting

7.3.1 Non-Serious Adverse Events

Non-serious AEs will be followed to resolution, or until the study ends, and reported to the Sponsor as requested, to the IRB according to IRB policies, to the DSMB as required, and to the FDA at least annually in the Annual Report. At the investigator/designee's discretion, subjects may be contacted up to 30 days after the study follow up period (Study Day 180) regarding non-serious AEs that are unresolved at Study Day 180.

AEs meeting the stopping criteria outlined in Section 7.5 of this protocol will be reported to the Sponsor following the SAE reporting guidelines.

7.3.2 Serious Adverse Events

Office of Clinical Research Policy and Regulatory Operations (OCRPRO)

All SAEs (regardless of relationship and whether or not they are also UPs) must be reported according to the sponsor's reporting plan by using the REDCap system. Deaths and immediately life-threatening SAEs must be reported to the CSO within 1 business day after the site becomes aware of the event. All other SAEs will be reported within 3 working days of notification of the SAE occurrence to:

- REDCap website: <https://crimsonredcap.cc.nih.gov/redcap/index.php>
- OCRPRO CSO [contact], [contact], E-mail: [contact]

SAEs that have not resolved by the end of the follow-up period are followed until final outcome is known. If it is not possible to obtain a final outcome for an SAE (e.g., the subject is lost to follow-up), the reason a final outcome could not be obtained will be recorded by the investigator on the AE CRF and according to the sponsor's reporting guidelines.

SAEs that occur after the study follow-up period (Study Day 180) that are reported to and are assessed by the investigator to be possibly, probably, or definitely related to study drug must be reported to the CSO.

DSMB

All SAEs will be reported by telephone (followed by written report), email, or fax within 1 working day of notification of the SAE occurrence to:

- The DSMB Executive Secretary: [contact], [contact], E-mail: [contact]

JHU Biosafety

All SAEs will be reported by telephone (followed by written report), email, or fax within 1 working day of notification of the SAE occurrence to:

- The JHU Institutional Biosafety Committee: [contact], [contact]

IRB Reporting

All SAEs will be reported to Johns Hopkins School of Public Health (JHSPH) IRB and University of Vermont (UVM) IRB as per guidelines, respectively for JHU and UVM as below:

- **JHSPH IRB Guidelines:**
 - JHSPH IRB [contact], [contact]
 - <https://www.jhsph.edu/offices-and-services/institutional-review-board/index.html> for updated reporting guidelines
- **UVM IRB Guidelines:**
 - Investigators are required to report AEs that fit the following criteria:
 - Report timelines are based upon of the time the investigator or site personnel becomes aware of them:
 - A local death report *within 48 hours*
 - All other local AEs should be reported promptly and not to exceed 7 days
 - Local AEs (whether or not they are serious), that are unexpected AND possibly, probably, or definitely related to study participation:
 - LOCAL ADVERSE EVENT is a negative side effect resulting from the study intervention that occurred to a subject enrolled at UVM, FAHC, or other research site under the jurisdiction of the UVM IRB.
 - UNEXPECTED: An event does not meet the criteria of unexpected if it is 1) included in the current protocol, drug/device brochure or the informed consent or 2) due to the subject's underlying disease or predisposing risk factors.
 - RELATED: An AE is considered to be related if there is a reasonable possibility that the event may have been caused by the protocol or study interventions. A related event has a strong temporal relationship to the drug, device, or intervention, and an alternative cause is unlikely. If it cannot be determined whether an event is related, it should be reported as "possibly related."
 - At UVM, all SAEs will be reported to the University of Vermont IRB (UVM IRB) according to UVM IRB guidelines.

- UVM IRB [contact], [contact]

7.3.3 Unanticipated Problems

Unanticipated Problems that are also adverse events must be reported to the CSO and sent by using the REDCap system no later than 7 calendar days of site awareness of the event. UPs that are not AEs are not reported to the Sponsor CSO.

Report UPs that are also adverse events to the CSO according to the sponsor's reporting guidelines or a local IRB UP form.

7.4 Sponsor's Reporting Responsibilities

Serious, unexpected, suspected adverse reactions (SUSARs) as defined in 21 CFR 312.32 and determined by the IND Sponsor will be reported to FDA and all participating Investigators as IND Safety Reports.

The Sponsor will also submit a brief report of the progress of the investigation to the FDA on an annual basis as defined in 21 CFR 312.33.

AEs that are also UPs will be summarized by the IND Sponsor and distributed to Investigators.

7.5 Halting Criteria

If a dose of ZIKV is considered unacceptably reactogenic, as defined below, additional inoculations will be suspended for all subjects and suspension of enrollment until the DSMB and study Sponsor (OCRPRO) have reviewed the data and recommend that enrollment and study agent administration be continued.

The Study PI/Protocol Chair and/or CSO will determine if the study should be halted. In addition, the FDA may halt the study at any time following review of any safety concerns. A local IRB may halt the study at their site.

Following administration of ZIKV, the following criteria will be used to define unacceptable reactogenicity of the ZIKV strain or dose:

1. One or more subjects experience an SAE (as defined in Section 7.1.6. in this protocol) that is determined to be possibly, probably, or definitely related to ZIKV (as defined in Section 7.2.4. in this protocol), **OR**
2. One or more subjects experience anaphylaxis that is possibly, probably or definitely related to ZIKV, **OR**
3. One or more subjects experience GBS that is possibly, probably or definitely related to ZIKV, **OR**
4. Two or more subjects experience the same objective physical finding of severity Grade 3 that is definitely, probably, or possibly related to ZIKV, with the exception of Grade 3 erythema at the injection site, as defined in Section 7.2.3. in this protocol, **OR**
5. Two or more subjects experience the same Grade 3 laboratory abnormality that is possibly, probably, or definitely related to ZIKV **OR**
6. Two or more subjects experience an ANC <500/mm³ for any duration¹ **OR**

7. Two or more subjects experience a ZIKV-like syndrome following administration of ZIKV, defined as infection² associated with fever **and 2 or more** of the following symptoms:

- a. Grade 2 or greater headache lasting ≥ 48 hours
- b. Grade 2 or greater photophobia lasting ≥ 48 hours
- c. Grade 2 or greater generalized myalgia lasting ≥ 48 hours

¹ These halting rules resulted from previous discussions between NIAID and the FDA on Phase 1 clinical trials of investigational live attenuated DENV vaccines (reference INDs 8463, 13730, and 13886).

² Infection is defined as recovery of ZIKVs from the blood, urine, cervico-vaginal secretions, or saliva of a subject and/or seropositivity or seroconversion to ZIKV.

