7 ADVERSE EVENT MONITORING

7.1 Definitions

7.1.1 Adverse Event

Any untoward or unfavorable medical occurrence in a human subject, including any abnormal sign (e.g. abnormal physical exam or laboratory finding), symptom, or disease, temporally associated with the subject's participation in the research, whether or not considered related to the research.

All AEs will be evaluated for severity, action taken, seriousness, outcome and relationship to the test article as described in Section [7.2](#) in this protocol.

If a diagnosis is clinically evident (or subsequently determined), the diagnosis rather than the individual signs and symptoms or lab abnormalities will be recorded as the AE. AEs will be collected through the 28-day period following each inoculation and any test article-related AEs identified in the 28-day post-inoculation period will be followed until resolution.

AEs are categorized as **solicited AEs and other AEs**. Solicited AEs include local reactogenicity, systemic reactogenicity, and laboratory events. Solicited AEs are those events that the clinician is specifically evaluating during each 28-day post-inoculation period, listed in **Table 8**. All AEs are evaluated using the Adverse Event Grading Table in [Appendix A](#), using severity definitions detailed in Section 7,

Table 9.

All abnormal laboratory findings will be reviewed on a routine basis by the PI to identify potential safety signals. An abnormal lab not included on the toxicity table should be assessed in a similar fashion to the criteria above.

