7.2.3 Determination of Severity

The investigator/designee will assess all AE severity using the following classifications.

Table 9: Severity Definitions

Severity	Defined
Grade 1 (Mild)	Event that is easily tolerated, may require 1 dose of medication/treatment
Grade 2 (Moderate)	Event that interferes with daily activity or requires more than 1 dose of medication/treatment
Grade 3 (Severe)	Event that prevents daily activity and requires medical intervention
Grade 4 (Life-threatening)	An adverse event that is deemed by the study clinician, the medical monitor, or an outside clinician caring for the subject to be a life-threatening event
Grade 5 (Death)	Any adverse event that results in the death of the subject

Solicited AE severity grading classifications are listed in

Table 10. All other AEs will be graded in severity using the Adverse Event Grading Table in [Appendix A: Adverse Event Grading Table1](#).

Table 10: Assessment of Solicited Adverse Events

Local Reactogenicity	Grade	Severity
Injection Site Tenderness	1	Event that is easily tolerated, may require 1 dose of medication
Injection Site Pruritis	2	Event that interferes with daily activity or requires > 1 dose of medication
Injection Site Pain	3	Event that prevents daily activity
	4	Life-threatening
Injection Site Induration	1	>0 - 20 mm
Injection Site Erythema	2	>20 - 50 mm
	3	>50 mm
	4	Life threatening
Systemic Reactogenicity	Grade	Severity
Fever (oral)	1	100.4° F – 101.4° F
	2	101.5° F – 102.4° F
	3	≥102.5° F
	4	Life-threatening
ZIKV-Like Rash	1	Rash is present but asymptomatic
	2	Rash is symptomatic (pruritis/pain) but does not interfere with function
	3	Rash is symptomatic and interferes with function
	4	Life-threatening
Headache	1	Event that is easily tolerated, may require 1 dose of medication/treatment
Retro-orbital pain		
Photophobia		
Non-purulent conjunctivitis	2	Event that interferes with daily activity or requires more than 1 dose of medication/treatment
Pruritis		
Fatigue	3	Event that prevents daily activity
Myalgia		
Arthralgia		
Muscle weakness	4	Life-threatening
Hypo-, areflexia		

Solicited Laboratory AEs	Grade	Severity
Leukopenia	1	2,500 – 3,500/mm ³
	2	1,500 – 2,499/mm ³
	3	1,000 – 1,499/mm ³
	4	<999/mm ³
Neutropenia (reduced ANC)	1	750 - 999/mm ³
	2	500 – 749/mm ³
	3	<500 mm ³
	4	Life-threatening
Thrombocytopenia (decreased platelets)	1	100,000 – 120,000/mm ³
	2	75,000 - 99,999/mm ³
	3	<74,999/mm ³
	4	Life-threatening

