Fatigue	Fatigue that is easily tolerated, may require 1 dose of medication/treatment	Fatigue that interferes with daily activity or requires >1 dose of medication	Fatigue that prevents daily activity
Myalgia	Myalgia that is easily tolerated, may require 1 dose of medication/treatment	Myalgia that interferes with daily activity or requires >1 dose of medication	Myalgia that prevents daily activity
Arthralgia	Arthralgia that is easily tolerated, may require 1 dose of medication/treatment	Arthralgia that interferes with daily activity or requires >1 dose of medication	Arthralgia that prevents daily activity
Muscle Weakness	Muscle weakness that is easily tolerated, may require 1 dose of medication/treatment	Muscle weakness that interferes with daily activity of requires >1 dose of medication	Muscle weakness that prevents daily activity
Hypo/areflexia	Hypo/areflexia that is easily tolerated, may require 1 dose of medication/treatment	Hypo/areflexia that interferes with daily activity of requires >1 dose of medication	Hypo/areflexia that prevents daily activity
Solicited Lab AEs	Grade I – Mild	Grade II – Moderate	Grade III - Severe
Leukopenia	2,500-3,500/mm ³	1,500-2,499/mm ³	1,000-1,400/mm ³
Neutropenia (Reduced ANC) ²	≥750-999/mm3	≥500-749/mm3	≤500/mm3
Thrombocytopenia (Reduced Platelets)	100,000 – 120,000/mm3	75,000 - 99,999/ mm3	≤74,999/mm3
Other Laboratory Values	Grade I – Mild	Grade II – Moderate	Grade III - Severe
Leukocytosis (Increased WBCs)	11,500 - 13,000/mm3	13,001 - 15,000/mm3	≥15,000 or <1,000/mm3

Event	Grade I – Mild	Grade II – Moderate	Grade III - Severe
Hemoglobin (female)	9.5 - 10.7 gm/dL	8.0 - 9.4 gm/dL	\leq 7.9 gm/dL
Hemoglobin (male)	11.0 - 12.5 gm/dL	9.0 – 10.9 gm/dL	\leq 8.9 gm/dL
PT	$>1.0 - 1.25 \times$ upper limit of normal (ULN)	$>1.25 - 1.5 \times$ ULN	$>1.5 \times$ ULN
PTT	$>1.0 - 1.66 \times$ ULN	$>1.66 - 2.33 \times$ ULN	$>2.33 \times$ ULN
ALT	$>1.25 - 2.5 \times$ ULN	$>2.5 - 5.0 \times$ ULN	$>5.0 \times$ ULN
Creatinine	1.5 - 1.7 mg/dL	$>1.7 - 2.0 \text{ mg/dL}$	$>2.0 \text{ mg/dL}$
Fibrinogen, Decreased	100 mg/dL to $<$ lower limit of normal (LLN)	50 - 99 mg/dL	$<50 \text{ mg/dL}$, or associated with gross bleeding, or associated with disseminated coagulation
Fibrinogen, Increased	$>\text{ULN}$ to 600 mg/dL	$>600 \text{ mg/dL}$	N/A
Creatine phosphokinase (CPK)	$\geq 4 \times$ ULN- 6 x ULN	$>6 \times$ ULN- 10 x ULN	$>10 \times$ ULN
Sodium: Hyponatremia	130 – 134 mEq/L	123 – 129 mEq/L	$<122 \text{ mEq/L}$

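### Halting rule 5 counts only Grade 3 laboratory results, so under Table 10 two related leukopenia cases at 900/mm³ would not trip it while two milder cases at 1,100/mm³ would

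*Combined protocol and SAP*

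**What the plan says.** Rule 5 in section 7.5 is met when "Two or more subjects experience the same Grade 3 laboratory abnormality that is possibly, probably, or definitely related to ZIKV". Rule 7 in the same list states its direction: "Grade 2 or greater headache lasting ≥ 48 hours". Direction is also stated in exclusion criterion 5 (section 4.2), in the Day 21 blood count condition (6.4.1.2) and in discharge criterion 3 (6.4.2).

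Leukopenia is a solicited laboratory AE (Table 8). Section 7.2.3 says "Solicited AE severity grading classifications are listed in" Table 10, and sends the remaining AEs to Appendix A. Table 10 grades the three solicited laboratory AEs as follows:

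| AE | Grade 3 | Grade 4 |
|---|---|---|
| Leukopenia | 1,000–1,499/mm³ | <999/mm³ |
| Neutropenia | <500/mm³ | life-threatening |
| Thrombocytopenia | <74,999/mm³ | life-threatening |

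Section 7.1.1 points elsewhere: "All AEs are evaluated using the Adverse Event Grading Table in" Appendix A. That table has no Grade 4 column; its footnote 1 assigns Grade 4 by judgement. Its Leukopenia row ends Grade III at 1,400/mm³. Its only entry for very low white counts is in the Grade III cell of the Leukocytosis row: "≥15,000 or <1,000/mm3".

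**The concern.** A halting rule should not stop at a moderate abnormality and stay silent at a worse one. Rule 5 does this for leukopenia if the words are followed as written: a count that falls below 1,000 leaves Grade 3 and no longer counts.

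Three things depend on the answer. When a rule is met, "additional inoculations will be suspended for all subjects" until the Data and Safety Monitoring Board (DSMB) and sponsor have reviewed the data. Section 3.1.2.2 makes the absence of a met halting criterion a condition for enrolling a cohort's second 7 subjects. Section 7.3.1 sends events that meet the stopping criteria to the sponsor on the SAE reporting route. The subjects are healthy volunteers who receive no direct benefit, so the stated threshold should give one answer for one laboratory value.

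**Working it through.** The plan gives no figure to reproduce. The check applies the cut-offs to example counts.

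**Inputs.** Rule 5: two or more related cases of the same laboratory abnormality at Grade 3. Rule 6: two or more subjects with ANC <500/mm³. Table 10 leukopenia: Grade 3 = 1,000–1,499, Grade 4 = <999.

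**Step 1: rule 5 under Table 10, and what rule 6 would need.** ANC is WBC times the neutrophil fraction, so ANC is below 500 when the fraction is below 500/WBC: 500/1,100 = 45.5%; 500/900 = 55.6%; 500/600 = 83.3%.

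| Two related cases (WBC) | Table 10 grades | Rule 5, literal | Neutrophil fraction needed for rule 6 |
|---|---|---|---|
| 1,100 and 1,100 | 3, 3 | trips | not needed |
| 1,100 and 900 | 3, 4 | does not trip | below 45.5% and below 55.6% respectively |
| 900 and 900 | 4, 4 | does not trip | below 55.6% in both |
| 600 and 600 | 4, 4 | does not trip | below 83.3% in both |

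**Step 2: how far rule 6 helps.** The documents give no neutrophil fractions; I assume a range of 30% to 70%.

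- At 900, ANC is 270, 360, 450, 540 and 630 for fractions of 30%, 40%, 50%, 60% and 70%. Rule 6 catches a pair at 900 only if both subjects are below 55.6%.
- At 1,100, ANC is 330, 440, 550, 660 and 770. A pair at 1,100 and 900 escapes both rules as soon as either subject exceeds his own limit.
- At 600, ANC is 180 to 420, so rule 6 catches a pair at 600 across the whole range.

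The two subjects need not share a fraction; the limits apply to each separately.

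**Step 3: the other solicited laboratory AEs.** Grade 3 neutropenia and thrombocytopenia have no floor, so a worse value stays in Grade 3 unless it is judged life-threatening. The gap is specific to leukopenia.

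**Step 4: Appendix A instead of Table 10.** Two cases at 900 trip rule 5 only if the low-count entry in the Leukocytosis row is taken to grade leukopenia. If it is a stray, Appendix A has no numeric grade below 1,000. Counts of 1,401–1,499 are Grade 3 in Table 10 but ungraded in Appendix A, so two cases at 1,450 trip rule 5 under Table 10 only. A count of exactly 999 has no grade in Table 10.

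**Step 5: after the change.** With Grade 3 or higher in rule 5, all four pairs in the table trip it. With Table 10 Grade 3 set to <1,500, all four are Grade 3 and trip it, unless a case is judged life-threatening; a related life-threatening event would then normally fall under rule 1.

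**The case against.** The best defence is that naming only Grade 3 is coherent. Nearly everywhere in Table 10, Grade 4 means life-threatening, and a related life-threatening event will usually be an SAE, which halts at a single subject under rule 1. Table 9 also makes Grade 4 a clinical decision, "deemed by the study clinician, the medical monitor, or an outside clinician", so a count of 900 that nobody judged life-threatening might be treated as Grade 3. A sensible investigator would probably count it. This places the fault in one table cell and not in the design of the rules, and that much stands. It does not close the gap: Table 10 assigns Grade 4 at <999 by number, and a count of 900 is not in itself the immediate risk of death that section 7.1.6 requires. The *medically important* route to an SAE is again a judgement.

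Other safeguards are real. The study PI/Protocol Chair or the sponsor's safety office decides on a halt, so the rules are not self-executing. Section 7.5.1 calls the rules a minimum and allows a halt on other grounds. The PI reviews abnormal laboratory findings routinely (7.1.1). Blood counts on Days 4, 8, 12 and 16 may also catch a subject at 1,000–1,499 on another day, if each draw is graded. The DSMB sees unblinded data before a cohort expands, but only once the first 7 reach Day 28, and both strains may be enrolling at the same time (3.1.6). These safeguards are discretionary or later; they reduce the consequence without making the rule correct.

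A reader might infer that the plan leaves the governing table wholly open. It does not: 7.2.3 is the specific text on severity and favours Table 10 for solicited AEs, and rule 4, just above rule 5, cites 7.2.3. The Appendix A differences are therefore secondary. A reader might also infer that rule 4 has the same hole. No such gap can be shown: every local and systemic reaction in Table 10 has Grade 4 as life-threatening, which falls largely under rule 1 with its stricter trigger.

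**Conclusion.** The concern holds, as a minor wording defect. Followed literally with Table 10, rule 5 stops for two related leukopenia cases at 1,000–1,499/mm³ but not when one or both of two such cases are below 999/mm³. Rule 1 catches these only if a case is judged an SAE. Rule 6 does so only if two subjects have ANC below 500, which for two cases at WBC 900 requires fractions below 55.6% in both. The mismatch between 7.1.1 with Appendix A and 7.2.3 with Table 10 is a separate, secondary inconsistency.

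Only cohorts 3 and 4 are affected (2 × 14 = 28 men, 2 × 10 = 20 of them ZIKV recipients), because all 14 women in each of cohorts 1 and 2 have been inoculated. The likelihood cannot be estimated: Tables 4 and 6 have no leukopenia row and show 1 neutropenia among 10 + 5 = 15 ZIKV recipients. The event is probably rare, and the documents do not support a claim that subjects have been or are likely to be harmed. The conclusion rests on a literal reading of rule 5; the 30–70% neutrophil range is an assumption used only to show how far rule 6 helps.

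**What to change.** 1. In rule 5, write *Grade 3 or higher*. Equivalent for this gap: set Table 10 leukopenia Grade 3 to <1,500/mm³ and Grade 4 to life-threatening, as for neutropenia and thrombocytopenia. The second option leaves the halting rules untouched.
2. Make the Appendix A leukopenia cut-offs match Table 10, so that 1,401–1,499 is graded. If a numeric Grade 4 is kept, write it as <1,000 so that 999 is graded too, and place it in the row or in footnote 1, since Appendix A has no Grade 4 column.
3. Delete the <1,000/mm³ entry from the Leukocytosis row.
4. Reword 7.1.1 to agree with 7.2.3: Table 10 for solicited AEs, Appendix A for the rest.

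Rule 4 needs no change. The cost is a short wording amendment with sponsor and IRB approval and DSMB review under section 8.5. A footnote in 7.5, attached to rule 6, says "These halting rules resulted from previous discussions between NIAID and the FDA", so the FDA should see the change. No data, visits or procedures are added. It should be in place before further inoculations in cohorts 3 and 4.

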7.5.1 Reporting a Study Halt

If a halting rule is identified by the Study PI/Protocol Chair and/or the CSO, a description of the adverse event(s) or safety issue will be reported by the Study PI within 1 business day of sponsor awareness to the other Site Investigator. The Study PI will notify the DSMB. The Site Investigators will notify their local IRBs. Safety data reports and changes in study status will be submitted to the applicable IRB promptly, in accordance with institutional policy. This constitutes a minimum criterion, and the decision to halt the trial may be made on the basis of any other criteria that, in the judgment of the investigators, FDA, IRB, DSMB, or Sponsor, indicate a potentially serious safety concern.

